Observational multicenter study

Number/code

Version 3.0

Date March 2018

Registry of COPD patients who undergo outpatient treatment or are under surveillance at outpatient polyclinic healthcare institutions of the Russian Federation in Moscow

PROTOCOL SYNOPSIS

Registry of COPD patients who undergo outpatient treatment or are under surveillance at outpatient polyclinic healthcare institutions of the Russian Federation in Moscow

Principal investigator:

[name], Doctor of Medicine, Professor, Head of laboratory, FSI «SRI of Pulmonology» of FMBA of Russia.

Sites, number of participants

At least (2000) patients at approximately 15 polyclinic sites in Moscow.

Investigators: pulmonologists of outpatient polyclinic care in Moscow

It is planned to enrol approximately 120 patients with diagnosed COPD **at each of approximately 15 polyclinic institutions of Moscow** (in total at least 2000 patients)

Study period

Planned study timeframes

Planned timeline for enrolment of first patient	Fourth quarter 2016
Planned timeline for enrolment of last patient	Second quarter 2018
Planned timeline for last patient out	Third quarter 2018
Planned timeline for database lock	Fourth quarter 2018
Planned timeline for final report preparation	First quarter 2019
Planned timeline for publication of results	Third quarter 2019

Medicinal product (name, dose, administration route) and concomitant therapy

Not applicable.

Background

Experts of the World Health Organization (WHO) estimated that approximately 210 mln. people worldwide suffer from COPD. In our modern age, COPD represents one of the leading

chronic diseases alongside with arterial hypertension, coronary heart disease and diabetes mellitus. They account for more than 30% among other human pathologies. COPD ranks fourth among causes of death worldwide, and is assumed to ascend to the third place by 2020. According to estimations using epidemiological markers, in the Russian Federation there are approximately 11 mln. people suffering from COPD. Whereas according to official statistics their total number in the Russian Federation amounts to only 2.4 mln. This is due to underdiagnosis and patients seeking medical attention too late, which result in detection of the disease at advanced stages when even the most modern treatment methods cannot delay steady progression of the disease. [1]

In the Russian Federation, diagnosis and treatment of COPD patients is performed primarily at community-based primary care outpatient polyclinic institutions. Every year in the Russian Federation there are approximately 100 thousands new cases of the disease diagnosed (statistics digest "Morbidity rates in adult population of Russia in 2012"). However, as a rule, COPD is diagnosed at advanced stages when complaints become a major problem for the patient. In many regions of the country, spirometric testing have still not been introduced into routine practice of primary care physicians, although on the positive side, in the recent years facilities of primary care outpatient polyclinic institutions have improved substantially.

In 2012 there were 2.7 mln. of COPD patients under surveillance at outpatient polyclinic institutions in the Russian Federation. However, we do not have at our disposal updated information regarding the prevalence of the disease in specific cities, distribution of these COPD patients by extent of airway obstruction. Data on pharmacotherapy are only approximate.

In developed countries, total economy expenses associated with COPD take 2nd place in the structure of pulmonary diseases after lung cancer, and if we consider direct expenses COPD takes the 1st place exceeding direct expenses for bronchial asthma 1.9-fold. Economy expenses per patient associated with COPD 3 times exceed those for an asthma patient. Scarce reports of direct medical expenses in COPD show that more than 80% of resources are spent on inpatient care and less than 20% – on outpatient care. It has been established that 73% of costs are associated with 10% of patients with severe disease. The highest economic losses are brought about by treatment of COPD exacerbations. In Russia, the economic burden of COPD taking into account indirect expenses, including absenteeism (absence from work) and presenteeism (less effective work caused by illness), amounts to 24.1 bln. roubles. [2]

Study conduction rationale

The majority of COPD patients in the Russian Federation seek medical attention from primary care physicians at outpatient polyclinic institutions. Physicians of these institutions can refer a patient for spirometric testing or to a pulmonologist (in this case, as a general rule, spirometry is also performed).

In the recent years in Europe registries of COPD patients have been created: Registry of COPD phenotypes in patients in Central and Eastern Europe (POPE Study- Phenotypes of COPD in Central and Eastern Europe) 2014-2015, Czech multicentre registry of COPD patients, started in 2014 (Czech Multicentre Research Database of COPD, Novotná et al. Czech multicenter research database of severe COPD. International Journal of Chronic Obstructive Pulmonary Disease 2014, 9: 1265-1274".)

Registry of COPD patients includes monitoring of the possible causes of the disease, prevalence of different phenotypes, assessment of disease progression, therapeutic approaches to disease treatment in real-life clinical practice, analysis of social and economical disease burden.

It is an important clinical and economical goal to arrange a registry of COPD patients who undergo outpatient surveillance at polyclinic institutions of Moscow, including description of patient clinical profile, diagnosis flow chart, therapeutic treatment tactics using different groups of medicinal products, compliance of used diagnostic and therapeutic approaches with current Federal clinical guidelines for COPD diagnosis and treatment, evolution of COPD prevalence parameters, monitoring of course of the disease.

In the absence of this information it is impossible to evaluate the quality of medical care provided to COPD patients in the Russian Federation or to plan any actions for treatment refinement.

Therefore, the purposes of the present study result from the necessity to perform the following:

- a) define clinical profile of COPD patients seeking attention and/or present in outpatient polyclinic medical care of healthcare system of Moscow (including diagnosis and therapeutic treatment tactics using different therapy regimens).
- b) determine the extent of the therapy conducted and its compliance with diagnosis, disease severity and phenotype
- c) define the disease burden (number of outpatient visits, hospitalizations, duration of days of disability, disability)

Investigation of the management of COPD patients in real-life clinical practice will enable us to obtain demographic and social data of the patients, study the natural history of COPD, perform monitoring of disease activity, evaluate the efficacy of therapy, demand for specialized treatment, perform pharmacoeconomic analysis, and develop standard statistical forms.

It is expected that it will be possible to use the results of the present study to assess % of different phenotypes of the COPD patients and treatment of people suffering from COPD not only in Moscow, but in other regions of the Russian Federation as well.

Study objectives

Primary objectives:

1. To describe the clinical profile of COPD patient who is under outpatient surveillance at polyclinic institutions of Moscow (including demographic data (age, gender, ethnicity, occupation), smoking status, disease duration, disease severity grade, distribution by disease phenotype, disease exacerbation rate in the setting of real-life clinical practice).

Secondary objectives:

1. Characterize distribution (percentage (%)) of COPD patients who seek attention from primary medical care physicians by severity of airway obstruction, by reversibility of

airway obstruction according to criteria described in Federal clinical guidelines for COPD diagnosis and treatment 2014.

2. To determine prevalence of the different disease phenotypes among outpatients: chronic bronchitis phenotype, emphysema phenotype, mixed phenotype, frequent exacerbator phenotype, Asthma+COPD phenotype (according to criteria described in Federal clinical guidelines for COPD diagnosis and treatment 2014).
3. To determine the percentage of patients with eosinophilic inflammation according to haematology results.
4. To describe treatment regimens prescribed to COPD patients depending on disease severity grade in the setting of real-life clinical practice.
5. To establish the percentage of medical prescriptions for treatment of COPD patients which comply with current Federal clinical guidelines for diagnosis and treatment of chronic obstructive pulmonary disease.
6. To establish prevalence and pattern of comorbidities in COPD patients.
7. To evaluate the disease burden based on the collected data concerning the duration of temporary disability, number of hospitalizations due to COPD exacerbations, number of outpatient visits concerning COPD patients under outpatient surveillance at polyclinic institutions of Moscow for three years.

Study design

The registry of COPD patients in fact represents non-interventional multicenter retrospective study including all COPD patients included into the registry retrospectively from patients medical records and newly diagnosed under outpatient surveillance at the selected polyclinic institutions of Moscow.

The registry will include all patients with registered diagnoses J40 - J44 according to ICD-10 with spirometry results confirming COPD diagnosis, who are at the study start under outpatient surveillance, and also newly registered patients diagnosed with COPD (ICD-10 J40 - J44, as confirmed by spirometry results) during the conduction of the registry program at the selected polyclinic institutions of Moscow (according to ICD: J40 - Bronchitis, not specified as acute or chronic, J41 - Simple and mucopurulent chronic bronchitis, J41.0 - Simple chronic bronchitis, J41.8 - Mixed simple and mucopurulent chronic bronchitis, J 42 - Unspecified chronic bronchitis, J 43 - Emphysema, J 44 - Other chronic obstructive pulmonary disease) based on regular (yearly) retrospective analysis of patient records with data entry into a consolidated database.

It is planned to enrol into the study approximately **2000** male and female patients over 40 years of age with diagnosed COPD (as confirmed by spirometry results).

The present observational multicenter descriptive study will be conducted in the setting of routine clinical practice of outpatient polyclinic institutions. There is no hypothesis to be tested in this study.

The study will be conducted in outpatient polyclinic institutions of the primary medical care system of Moscow. Pulmonologists of the primary medical care system will be engaged as investigators. These are the physicians, whom the patients with tentative COPD diagnosis are referred to in the Russian Federation and who within the scope of their responsibilities have access to source medical records and who evaluate the quality of diagnosis and extent of treatment prescribed to COPD patients.

The present study is observational therefore it does not require a treatment regimen or directions for patient management. The patients receive medical care in line with routine practice for treatment of this disease in the Russian Federation. Patient participation in the study should not in any way affect the principles and extent of treatment received by the patient according to routine clinical practice.

Physicians-investigators will enter into the study the information (data) concerning COPD patients, both those already registered at the selected medical treatment and preventive care institution, and newly registered patients as they seek attention at the outpatient polyclinic institutions.

The main purpose of the present study consists in collection of data concerning COPD patients who under surveillance at outpatient polyclinic institutions of Moscow using patient medical records and their medical history. This protocol does not specify any obligatory visits or examinations.

Patient data will be entered into the registry de-identified. The patients will be identified by their screening number and initials. Then the Physician-investigator will evaluate patient compliance with inclusion criteria. The study will enrol patients meeting all the inclusion criteria and not having any of the exclusion criteria.

Only the physician who enters patient data into the regional COPD registry possesses patient contact information, and henceforth only this physician will enter de-identified patient data according to study design. This physician does not influence the choice of examination extent, treatment strategy and medication.

Study variables

Primary variables

1. Description of the clinical profile of COPD patient under outpatient surveillance at polyclinic institutions of Moscow (including demographic data (age, gender, ethnicity, occupation), smoking status, disease duration, disease severity grade, distribution by disease phenotype, disease exacerbation rate in the setting of real-life clinical practice)

Secondary variables:

1. Percentage of patients with different disease phenotypes among outpatients
2. Percentage of prescriptions of medicinal products to COPD patients depending on disease severity grade in the setting of real-life clinical practice

Number/Code:
Version:
Date:

3. Distribution (%) of COPD patients who seek attention from primary medical care physicians by severity of airway obstruction (according to Federal clinical guidelines for diagnosis and treatment of COPD patients, 2014)
4. Mean number of exacerbations requiring medical attention (outpatient prescription of oral corticosteroids and/or antibiotics) in the last year in COPD patients
5. Mean number of hospitalizations in the last year in COPD patients
6. Percentage of patients with eosinophilic inflammation
7. Description of treatment regimens prescribed to COPD patients depending on disease severity grade in the setting of real-life clinical practice
8. Percentage of prescriptions for treatment of COPD patients in line with the current Federal clinical guidelines for diagnosis and treatment of chronic obstructive pulmonary disease
9. Disease burden based on the collected data concerning the duration of temporary disability, number of hospitalizations due to COPD exacerbations, outpatient visits concerning COPD during follow-up

Statistics

Descriptive analysis approach will be applied for analysis of the study objectives. Descriptive statistics will be used for analysis of the study population, baseline and clinical data.

Descriptive statistics will include frequency tables (n, mean, median, standard deviation, minimum and maximum for continuous variables; n, frequency and percentage for categorical variables). Percentages will be evaluated together with 95% confidence intervals (in appropriate cases).

TABLE OF CONTENTS

	PAGE
TITLE PAGE	1
PROTOCOL SYNOPSIS	2
TABLE OF CONTENTS	8
LIST OF ABBREVIATIONS	11
1. INTRODUCTION	12
1.1 Background	12
1.2 Study rationale	13
2. STUDY OBJECTIVES	14
2.1 Primary study objective	14
2.2 Secondary objectives	14
3. STUDY PLAN AND PROCEDURES	15
4. PATIENT POPULATION	17
4.1 Physicians-investigators	17
4.2 Selection criteria for COPD patients	18
4.2.1 Inclusion criteria for patients with diagnosed COPD	18
4.2.2 Exclusion criteria for patients with COPD risk factors and for patients with previously diagnosed COPD	18
5. PATIENT WITHDRAWAL FROM THE STUDY	18
5.1 Withdrawal criteria	18
5.2 Procedures for patient withdrawal from the study	18
6. PATIENT TREATMENT	19
6.1 Treatment strategy in observational studies	19
7. STUDY CONDUCTION	19
7.1 Description of the visits	19
8. PARAMETERS COLLECTED FOR STUDY, ASSESSMENT AND REGISTRATION METHODS	20
8.1 Primary endpoints	20
8.2 Secondary endpoints	20
8.3 Economic health assessment	21
8.3.1 Disease burden assessment	21
8.3.2 Other parameters for disease burden assessment	21
9. SAFETY ASSESSMENT	21
9.1 Definitions	21

Number/Code:
Version:
Date:

9.1.1	Definition of an adverse event (AE).....	21
9.1.2	Definition of a serious adverse event (SAE).....	22
9.2	Non-interventional studies without specific safety assessment objectives	22
9.3	Non-interventional studies with specific safety assessment objectives	22
9.4	Safety data reporting	23
9.4.1	Adverse event reports.....	23
9.4.2	Reports of unexpected adverse events during use of medicinal products for human use.....	23
9.4.3	Registration of spontaneous reports regarding adverse events	23
10.	ETHICS	24
10.1	Committee on ethical review for clinical studies (EC)	24
10.2	Informed consent.....	24
10.3	Patient data confidentiality	24

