4. PATIENT POPULATION

4.1 Physicians-investigators

The present study is non-interventional (an observational, multicenter, descriptive study). Randomly selected polyclinic institutions of Moscow will take part in the study and enrol into the registry 2000 COPD patients.

The patient population includes male and female patients over 40 years of age, smokers or ex-smokers, under outpatient surveillance at polyclinic institutions of Moscow with diagnosis codes according to ICD J40 - J44 and diagnosed COPD, as confirmed by spirometry results.

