10.1 Committee on ethical review for clinical studies (EC)

Before study start, written favourable conclusion of EC (ethics committee) should be received concerning the study protocol, ICF and CRF. If in the course of the study any amendments to these documents are made, written approval should be received before their implementation.

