10.3 Patient data confidentiality

The present study is retrospective and is thus based on data which will be retrieved from archives kept by the investigators. Collection of patient data will be performed by the personnel of the clinical institution; as these data will not include any information enabling identification of the patient, in the present study there is no need to obtain patient informed consent (according to the personal data protection law of the Russian Federation).

Identification number assigned by the investigator to each patient will be used instead of the patient's name in order to protect patient's personal data during reporting of adverse events and/or other study-related data. Identification number will consist of four digits, the first two will stay the same for all the patients from the same investigational site (site code), and the last two digits will be individual for this patient, whose medical records will be analysed at the site (patient code).

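### The planned site and per-site numbers give 1800 patients against a stated minimum of 2000, and the two-digit patient code cannot number the 120 patients planned per site

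*Combined protocol and SAP*

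**What the plan says.** **Enrolment.** The synopsis (Sites, number of participants) opens with "At least (2000) patients at approximately 15 polyclinic sites in Moscow". It then adds "It is planned to enrol approximately 120 patients with diagnosed COPD" at each of about 15 institutions and, in that same sentence, repeats 2000 as a minimum. The Study design part of the synopsis and Section 3 make the total approximate. Section 4.1 gives it without a qualifier: the polyclinics will "enrol into the registry 2000 COPD patients". Section 12.5 says that no sample size was calculated, so the protocol offers no other derivation of 2000. The Study design text also says "The registry will include all patients with registered diagnoses J40 - J44", subject to confirmation by spirometry, and Section 3 agrees. The figure of 120 is therefore an expectation and not a cap.

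**Identifiers.** Section 10.3 says "Identification number will consist of four digits". The first two are a site code shared by all patients of a site, and "the last two digits will be individual for this patient". This number stands in for the patient's name in adverse-event reports and other study data. Elsewhere, in the synopsis and Section 3, the text reads "The patients will be identified by their screening number and initials". No format is given for the screening number, and nothing says how it relates to the Section 10.3 number or which of the two is the database key.

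**The concern.** These are two separate inconsistencies, and correcting one leaves the other in place.

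The first is that the stated size does not follow from the stated inputs. A reader cannot tell whether the target is 1800 or 2000, or whether 2000 is a floor or a rough figure. The study tests no hypothesis, so no power or error rate depends on the answer. What is at stake is a coherent statement of the planned size.

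The second matters more. The only identifier whose format is defined has fewer values per site than the patients planned there. A site that follows the rule and reaches its planned enrolment must reuse a number, invent a longer one or stop numbering. A reused number could attach a paper CRF or an adverse-event report to the wrong patient. Section 3 says that only the entering physician holds patient contact information, so such a clash may have to be resolved at the site.

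**Working it through.** **Inputs.** About 15 sites, about 120 patients per site and a minimum total of 2000 (synopsis); two digits for the site and two for the patient (Section 10.3).

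**1. The total**

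- Sites × patients per site = 15 × 120 = 1800. The stated 2000 is not reproduced.
- Shortfall: 2000 − 1800 = 200, and 200/2000 = 10%.
- What would reach 2000: 2000/15 = 133.3, so 134 per site at 15 sites (15 × 134 = 2010); 2000/120 = 16.7, so 17 sites at 120 (17 × 120 = 2040); or 16 × 125 = 2000.
- Effect on precision: the worst-case 95% half-width for a percentage is 1.96 × √(0.25/n), assuming simple random sampling. At n = 2000 it is 2.19 points; at n = 1800 it is 2.31 points. The difference is 0.12 points. Patients are grouped within polyclinics, so both true widths will be larger, but the comparison supports nothing beyond negligible.

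**2. The patient code**

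- Two digits give 10² = 100 codes per site. If 00 is not used (an assumption; the protocol does not say), there are 99.
- Capacity at 15 sites: 15 × 100 = 1500, or 15 × 99 = 1485 without 00.
- Sites needed to hold 2000 patients: 2000/100 = 20; without 00, 2000/99 = 20.2, so 21.
- The limit lies in how the digits are split. Four digits hold 10⁴ = 10,000 numbers in all, but no site can use more than 100 of them.

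Patients left without a unique number:

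| Scenario | Per site | Overall | Share |
|---|---|---|---|
| 15 × 120 (the protocol's figures) | 120 − 100 = 20 (21 without 00) | 300 (315) | 20/120 = 16.7% (17.5%) |
| 16 × 125 (illustration reaching 2000) | 125 − 100 = 25 (26) | 400 (416) | 25/125 = 20.0% (20.8%) |
| 15 × 134 (illustration reaching 2000) | 134 − 100 = 34 (35) | 510 (525) | 34/134 = 25.4% (26.1%) |

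Only the first row uses the protocol's own site and per-site figures. The other two show that raising enrolment per site to close the gap in part 1 widens the gap in part 2.

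**The case against.** On the total, both inputs are approximate, a small upward shift reaches 2000, and a registry that takes all eligible patients need not have a total equal to the product of two planning averages. No analysis turns on 1800 versus 2000. All of this stands, and it limits the first part to a consistency correction. It does not remove the inconsistency, because 2000 is worded as a minimum in the very sentence whose figures give 1800. The difference between an approximate and a plain 2000 is editorial; only the minimum differs in meaning.

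On the code, the harm is conjectural. If the screening number is the database key, CRFs need not be duplicated. Sections 9.2 and 9.3 rule out proactive safety collection, and Section 9.4.3 sends spontaneous reports on the regulator's own form, so the adverse-event route is narrow. Enrolment was also due to end in the second quarter of 2018, soon after this protocol version (March 2018), so large sites may already have found a workaround. These points show that mis-linkage is unproven, and that stands. They do not supply the missing codes. The screening number has no stated format or role. Sections 3 and 7.1 do collect adverse drug reactions at enrolment. A second site code for a large site would contradict Section 10.3, which keeps the first two digits constant within a site.

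**Conclusion.** Both parts hold.

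1. The stated inputs give 1800, which is 200 patients (10%) below the stated minimum. Approximation could absorb this, and the effect on precision is about 0.12 percentage points in the worst case under simple random sampling. It is a wording correction only.
2. The two-digit patient code is too short for the planned enrolment. On the protocol's own figures, 20 patients per site and 300 overall (16.7%) lack a unique number, or 21 and 315 (17.5%) if 00 is unused. No reading of about 15 sites brings 2000 patients within the limit, since that takes at least 20 sites. The shortage is certain if sites follow Section 10.3 and reach 120. Duplicate or mis-linked records are a risk, which depends on what sites did in practice and on which identifier is the key; the protocol settles neither.

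The second part is the reason to amend. The first can be corrected in the same amendment.

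**What to change.** **Enrolment figures.** Make sites, patients per site and total agree. Either restate the total as about 1800, or keep 2000 and change the inputs, for example to about 134 per site at 15 sites or 125 at 16. If 2000 is the real target, changing the inputs is the smaller edit, because that total recurs in both parts of the synopsis and in Sections 3 and 4.1. Restating it as 1800 makes the stated size 10% smaller. Use one total and one qualifier throughout.

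**Identifier.** In Section 10.3, define five digits: two for the site and three for the patient. That covers 120, 125 or 134 per site. Extend existing numbers by zero-padding (0107 becomes 01007), check for duplicates before database lock, and renumber only those found. State whether this number is the database key and how it relates to the screening number in the synopsis and Section 3.

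**Cost.** A short amendment; Section 10.1 requires that "written approval should be received before their implementation". Beyond that, a wider identifier field wherever the number is stored and a list mapping old numbers to new. CRFs are on paper according to the list of abbreviations, so the mapping list can avoid relabelling them. The duplicate check remains useful late in enrolment, because lock was planned for the fourth quarter of 2018 and Section 12.3 places all analysis after it.
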